6.3 PATIENT SETS ANALYSED

The following nested patient sets are defined:

- Randomised set (RS):

This patient set includes all patients who signed informed consent form and were also randomised, regardless whether the patient was treated with study medication or not.

- **Treated set (TS):**

This patient set is nested within RS and includes all patients who were dispensed study medication and were documented to have taken any dose of study medication. TS will be used for patient disposition, demographics and baseline disease characteristics, concomitant therapies, treatment compliance, treatment exposure and safety analyses (including AEs and vital signs).

- **Full analysis set (FAS):**

This patient set is nested within TS and includes patients who had baseline measurement and at least one post-baseline measurement for the primary endpoint. The FAS will be used for the efficacy analyses. Assignment to the FAS will be done after implementation of any data handling rules which set measurements to missing.

- **Per protocol set (PPS):**

This patient set is nested within FAS and includes only patients who had no important PVs which are specified to be excluded from the PPS ([Table 6.3: 1](#)). The final decision regarding which patients are excluded from PPS will be made at BRPM prior to data unblinding.

If the number of patients in PPS is less than 90% of the number of patients in FAS, the primary analysis for the primary endpoint will also be performed on the PPS as supportive analyses.

Table 6.3: 1 Patient sets analysed

Class of endpoint	Patient Sets		
	TS	FAS	PPS
Primary endpoint		primary analysis	supportive analysis*
Secondary endpoints		X	
Further endpoints		X	
Safety endpoints	X		
Demographic/baseline endpoints/exposure	X		

* Performed only when the number of patients in PPS is less than 90% of the number of patients in FAS as sensitivity analysis.

6.5 POOLING OF CENTRES

This section is not applicable because centre/country is not included in the statistical model.

6.6 HANDLING OF MISSING DATA AND OUTLIERS

As noted in the protocol, in general, missing data at a given visit will be imputed by the available data from the patient at that visit and completely missing visits will be handled through the statistical model.

Completely missing visits not due to worsening of study disease will not be imputed and will stay as missing, because such missing data are considered as randomly missing data and will be handled in the mixed model repeated measures model.

Completely missing visits due to the patient discontinuing due to worsening of study disease will be imputed with the least favourable prior visit during that period.

It could happen that a patient needed therapy for COPD symptoms at a clinic visit. This therapy was entered on the rescue medication electronic Case Report Form (eCRF). This may or may not be the rescue medication provided by Boehringer Ingelheim (BI). For purposes of the imputation rules this will be termed “rescue medication” regardless of whether or not it was BI-supplied rescue medication.

The following rules are used for exercise data:

In situations where the full 3-min of exercise was completed:

- Measurements of Borg breathing discomfort scale, [REDACTED] which are missing for the 3 minute time point will be imputed using the last non-missing observation during exercise (but not non-missing measurements at rest) for that visit.
- Measurements of Borg breathing discomfort scale, [REDACTED] which are missing for all other time points during exercise will not be imputed (i.e. left as missing).

In situations where exercise is terminated prematurely:

- Borg breathing discomfort [REDACTED] scores will be imputed from end-of-exercise value for all time points beyond the exercise termination (including the 3 minute time point).

[REDACTED]

In addition, the following rules apply:

[REDACTED]

- If rescue medication was used prior to exercise testing or if the time of rescue medication use is unknown, measurements taken at rest and during exercise, i.e., - Borg scale of breathing discomfort, [REDACTED] blood pressure, and IC will be set to missing and not imputed. If rescue medication was used during exercise testing, measurements of Borg scale of breathing discomfort [REDACTED] will be set to missing for those time points after the first use of rescue medication and imputed using the worst non-missing observation during exercise (but not non-missing measurements at rest) for that visit before rescue medication use.

The following rules will be used for spirometry data which were collected at Visits 4, 5, 6, 7, 8, and 9:

- Since there is only one spirometry measurement at each on-treatment clinic visit, rescue medication use on or before the spirometry measurement or rescue use with unknown time will both result in all spirometry measurements for the visit being set to missing. In these cases the entire visit will be imputed using the least favourable prior non-missing measurement from previous visits during that period.
- If the spirometry measurement for a visit is completely missing because a patient discontinued due to worsening of study disease, then all data for this visit will be imputed with the least favourable prior observation from previous visits during that period.
- Randomly missing spirometry measurements at Visits 5, 6, 8 and 9, e.g., due to a mechanical failure, will not be imputed.

Also,

[REDACTED]

- For endpoints with two period baselines, if one period baseline is missing, it will be imputed by the other period baseline.

- For CRQ-SAI, at visits where dyspnoea activities were selected differently than the baseline (at visit 4), those dyspnoea activity values will be set as missing values.

Missing or incomplete AE dates are imputed according to BI standards (see “Handling of missing and incomplete AE dates”) [\(2\)](#).

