#### 10. Measurements during ISWT:

BORG measurements conducted at rest, every 2 minutes during exercise and at the end of exercise. Refer to Appendix 10.5 for further details.

Page 10 of 137

- IC to be conducted at rest, every 2 minutes during exercise and at the end of exercise using mobile cardiopulmonary exercise equipment. IC measurements are to be done after the BORG measurements. Refer to Appendix 10.7 and manual of procedures for further details.
- 11. V2 3min CSST: Speed to be determined at visit 2 by conducting up to three tests at select speeds.
- 12. V3 3min CSST: Practice test for the 3min CSST at speed selected from V2.
- 13. 3min CSST timing V4 and V7: 3min CSST conducted prior to dosing (period baseline).
- 14. 3min CSST timing V5, V6, V8 and V9: 3min CSST conducted 2 hours post-dose (+15 minutes).
- 15. BORG measurements during 3min CSST: BORG measurements conducted at rest, 1, 2, 2.5 minutes during exercise and at 3min or end of exercise (if 3 minutes not achieved). Refer to Appendix 10.5 for further details.
- 16. Inspiratory Capacity measurements: IC measurements performed at rest and at end exercise during 3min CSSTs using mobile cardiopulmonary exercise equipment. IC measurements are to be done after the BORG measurements. Refer to Appendix 10.7 and manual of procedures for further details.
- 19. BDI score: Score <8 is required for inclusion.
- 20. Reversibility Testing: Pre- and post-bronchodilator FEV1 and FVC (400 μg salbutamol (albuterol)). [note: reversibility is not an inclusion criterion]
- 21. Baseline spirometry measurements: Conducted prior to exercise testing.
- 22. Post-dose FEV1 and FVC: 1 hr post-dose (±10 minutes) and prior to exercise testing
- 23. Vital Signs: Immediately prior to PFTs.
- 24. Medication Use: Measured using the counter on the Respimat® device.
- 25. Telephone Contacts: Site staff will telephone the patient 1-2 days prior to clinic visits to remind them of medication washout and any other requirements.
- 26. To be completed in the event of any clinically relevant findings at the End of Trial (EOT) visit.

Proprietary confidential information © 2016 Boehringer Ingelheim International GmbH or one or more of its affiliated companies

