Traditional constant work rate exercise tests (e.g. endurance shuttle walking, constant work rate cycle ergometry) are conducted to the point of symptom limitation, which presents challenges regarding the evaluation of symptoms during exercise due to the open-ended nature of these tests. To address this issue, a novel exercise methodology, the 3min CSST, has been developed that allows specific focus on the assessment of activity-related breathlessness (using the MBS-S) at specific pre-defined timepoints in patients with COPD. The feasibility and reproducibility of the 3min CSST in providing a standardized physical stimulus and a measurable level of breathlessness in patients with moderate to severe COPD has been reported [R15-4319]. In one study, the responsiveness of the 3min CSST to bronchodilation was confirmed, with a statistically significant reduction in the intensity of breathlessness with ipratropium bromide compared to placebo [P12-12739].

Breathlessness or dyspnea is characterised as "a subjective experience of breathing discomfort that consists of qualitatively distinct sensations that vary in intensity [and] vary in their

<sup>1 In this protocol, the terms "breathlessness" and "dyspnea" are used interchangeably as the general term to describe the subjective experience of breathing discomfort [R15-4208]; the specific sensation that patients will be asked to attend to during the 3 min CSST is "breathing discomfort" (see Appendix 10.5). In the ATS statement on dyspnea, keywords are identified as "breathlessness", "shortness of breath" and "respiratory sensation".

BI Trial No.: 1237.28

c03207491-01 Trial Protocol Page 21 of 137

Proprietary confidential information © 2016 Boehringer Ingelheim International GmbH or one or more of its affiliated companies

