#### 3.3.2 Inclusion criteria

1. All patients must sign an informed consent consistent with International Conference on Harmonisation - Good Clinical Practice (ICH-GCP) guidelines prior to participation in the trial, which includes medication washout and restrictions.

2. All patients must have a diagnosis of COPD [P11-05865] and must meet the following spirometric criteria:

Patients must have relatively stable airway obstruction with a post-bronchodilator  $30\% \le \text{FEV}_1 < 80\%$  of predicted normal (European Coal and Steel Community (ECSC), [R94-1408] see Appendix 10.3 for ECSC predicted normal equations); GOLD 2 - 3, [P11-05865] and a post-bronchodilator FEV1/FVC < 0.70 at visit 1.

- 3. Male or female patients, between 40 and 75 years of age (inclusive) on day of signing informed consent.
- 4. Patients must be current or ex-smokers with a smoking history of more than 10 pack-years (see Appendix 10.3 for calculations). Patients who have never smoked cigarettes must be excluded.
- 5. Patients with a score on the Baseline Dyspnea Index (BDI) < 8 at visit 0.
- 6. Patients with hyperinflation at rest, defined as Functional Residual Capacity (FRC) >120% predicted at visit 1 (see Appendix 10.7).
- 7. BORG dyspnea score ≥4 at the end of 3min CSST at visit 2 (refer to Appendix 10.4.2.2 and manual of procedures for further details).
- 8. Patients must be able to perform technically acceptable pulmonary function tests (PFTs) (spirometry and body plethysmography), must be able to complete multiple shuttle tests during the study period as required in the protocol.
- 9. Patients must be able to inhale medication in a competent manner from the Respirat® inhaler (Appendix 10.1) and from a MDI.

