## 5. VARIABLES AND THEIR ASSESSMENT

#### 5.1 TRIAL ENDPOINTS

#### 5.1.1 Primary Endpoint

The primary endpoint is the change from baseline in intensity of breathlessness measured using the MBS-S at the end of the 3min Constant Speed Shuttle Test (CSST) after 6 weeks of treatment.

Change from baseline is defined as change from patient baseline. See Section 7.3.1.

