### 10.4.2 Shuttle Test

Shuttle tests will be performed in all patients of this trial. Selection of sites is based on past experience with the test and/or the availability of suitable infrastructure and qualified personnel.

The shuttle test is performed on a flat, straight walking track, in a quiet treatment area that is at least 12 meters in length and approximately 2 meters wide, and clear of hospital traffic and obstacles. The standard instructions are given by trained site staff. Patients are required to walk, jog or run back and forth, in loops of 10 meters long. Cones are placed half a meter from the end, so they are 9 meters apart. The patient must keep pace with the pre-recorded auditory signal such that he/she completes a turn as each audio signal sounds.

[figure not shown]

Figure 10.4.2:1: Set up for the shuttle test

During the test oxygen saturation and heart rate will be monitored using a pulse oximeter (fingertip or ear lobe sensor). Patients will also wear mobile cardiopulmonary exercise equipment. A chair should be placed in the immediate surroundings of the track for the patient to rest before and at the end of the test.

For the ISWT at visit 1, the end of the test will be signaled

- a) by the patient, when he feels too breathless or fatigued to continue at the required speed.
- b) by the operator when the patient fails to keep up to auditory signals after repeated warnings and encouragements (patient is more than 0.5 meter from the cone at the beep) and is unable to catch up within 3 shuttles.
- c) when the patient is unable to continue safely (in the opinion of the supervising technician or physician).

For the 3min CSST, the end of the test will be signaled

- a) by the patient, when he feels too breathless or fatigued to continue at the required speed.
- b) by the operator when the three minutes of testing is completed.
- c) by the operator when the patient fails to keep up to auditory signals after repeated warnings and encouragements (patient is more than 0.5 meter from the cone at the beep) and is unable to catch up within 3 shuttles.
- d) when the patient is unable to continue safely (in the opinion of the supervising technician or physician).

Boehringer Ingelheim

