Table 6.2: 1 Important protocol violations

Category / Code	Description	Requirements	Excluded from	Automatic/ Manual
A	Entrance criteria not met			
	A1	Inclusion criteria not met	Inclusion Criteria 2-9 not met as specified in the protocol.	Exclude from PPS*: 2-9
	A2	Exclusion criteria not met	Exclusion Criteria 1-30 not met as specified in the protocol	Exclude from PPS*: 3, 4, 8-12, 14-25, 29, 30
B	Informed consent			
	B1	Informed consent not available/not done	Informed consent date missing; no signature on ICF.	All
	B2	Informed consent too late	Date of informed consent was after the date of any study-related procedure, or a patient signed the correct version of the ICF after Visit 0. If date of informed consent equals to date of Visit 1, such cases will be discussed at MQRM/BRPM/DBL meetings.	None
C	Trial medication and randomisation			
	C1	Incorrect trial medication taken	Not throughout study; could be at a clinic visit or between clinic visits. External vendor will check before unblinding.	PPS (decision at BRPM)
	C2	Randomisation order not followed	Throughout the study	PPS
	C3	Non-compliance with study medication		
	C3.1	Serious non-compliance with study medication as reported in monitoring report or manual PV spreadsheet	Decision at BRPM/MQRM.	PPS if at Visit 6 or 9
	C4	Medication code broken inappropriately	To be discussed and decided during MQRM/BRPM. Only inappropriate code breaks are IPVs (e.g. unblinding by Global Pharmacovigilance is not).	PPS

Table 6.2: 1 (continued) Important protocol violations

Category / Code		Description	Example/Comment	Excluded from	Automatic/ Manual
D		Concomitant medication			
	D1	Improper medication washout at baseline visit or primary endpoint visit(s)	Visit 4,6,7,9. Decision at BRPM	PPS	Automatic and Manual
	D2	Prohibited medication use during study	Check CT. Decision at BRPM.	PPS if in the week prior to Visit 4,6,7,9	Automatic and Manual
F		Incorrect timing			
	F3	Primary endpoint recorded outside time window			
	F3.5	Constant speed shuttle test <1 hour or >3 hours after inhalation	Only at Visits 6, 9	PPS	Automatic
Z		Other			
	Z1	Serious GCP non-compliance	Manual PVs reported by CML/CRA which are considered as important. Carefully reviewed, described and documented in DBL meeting minutes.	PPS	Manual

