	Z2	Other PV affecting efficacy and possibly safety	Additional PV identified through monitoring which impacts the primary analysis and possibly patient's rights or safety. Carefully reviewed and documented in BRPM minutes and comment field of IPV ADS.	PPS	Automatic and Manual
	Z3	Other PV affecting safety only	Additional PV identified through monitoring which impacts patient's rights or safety. Carefully reviewed and documented in BRPM minutes and comment field of IPV ADS.	None	Automatic and Manual

KEY: CT = Concomitant Therapy, BRPM = Blinded report planning meeting, CML = Local Clinical Monitor, CRA = Clinical Research Associate, ICF = informed consent form, MQRM = Medical Quality Review Meeting, PPS = Per protocol set, DBL = Data Base Lock, ADS = Analysis Data Set

*Final decision will be discussed and determined prior to database lock.

Note: Missing visits, evaluations, and tests are considered as missing data, but not protocol deviations.

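### Does using the stopping score as the 3-minute Borg score leave the primary endpoint without a needed check?

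*SAP*

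**What the plan says.** Protocol 5.1.1 sets the primary endpoint as the change from baseline in breathlessness "measured using the MBS-S at the end of the 3min Constant Speed Shuttle Test (CSST) after 6 weeks of treatment". The period baseline in Protocol 7.3.1 is likewise the end-of-test rating. Footnote 15 of the Flow Chart fixes the rating times: "BORG measurements conducted at rest, 1, 2, 2.5 minutes during exercise and at 3min or end of exercise (if 3 minutes not achieved". Appendix 10.4.2 lists how a walk can end. Completing 3 minutes is one way. Another is a stop "by the patient, when he feels too breathless or fatigued to continue at the required speed".

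SAP 6.6 covers the early stop: Borg "scores will be imputed from end-of-exercise value for all time points beyond the exercise termination (including the 3 minute time point". SAP 7.4 gives one readable model for the primary endpoint. SAP 6.3 repeats it on the per-protocol set only if that set is smaller than 90% of the full analysis set.

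Protocol 5.1.2 makes the ratings at 1, 2 and 2.5 minutes secondary endpoints. SAP 6.7 pairs each with a period baseline at the same minute, and SAP 7.5.2 applies the primary model to them.

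**The concern.** Protocol 2.1 justifies the 3-minute test because symptom-limited tests are hard to interpret, whereas this one "allows specific focus on the assessment of activity-related breathlessness (using the MBS-S) at specific pre-defined timepoints". A walk stopped for breathlessness is again symptom-limited, and its last rating is taken after less exercise than a completed walk. If breathlessness would have kept rising, the stopping score understates the 3-minute score. Were early stops more common on tiotropium, the combination's benefit would be diluted; were they more common on the combination, it would be exaggerated.

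The per-protocol repeat does not help. The note under SAP Table 6.2:1 reads "Missing visits, evaluations, and tests are considered as missing data, but not protocol deviations". The timing code is about dosing ("Constant speed shuttle test <1 hour or >3 hours after inhalation"). The requirement that patients "must be able to complete multiple shuttle tests during the study period as required in the protocol" is an entry criterion. No readable code targets an early stop on treatment, and no readable table counts such stops by treatment. So the rule looks as if it bears on the primary result with nothing to show whether it mattered.

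**Working it through.** **1. Does the rule depart from the endpoint?** Set the provisions side by side:

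- Endpoint (Protocol 5.1.1) and period baseline (Protocol 7.3.1): rating at the end of the test.
- Final scheduled rating (Flow Chart, footnote 15): at 3 minutes, or at the end of exercise if 3 minutes are not reached.
- SAP 6.6: the end-of-exercise rating fills the 3-minute slot.

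For the primary endpoint, SAP 6.6 places an observed value in the analysis slot where the protocol puts it. Nothing unobserved is guessed. The score the patient might have given at 3 minutes belongs to a different question.

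**2. The plan's own figure.** Inputs from Protocol 7.7: difference 0.5, SD of the within-patient difference 1.776, two-sided alpha 0.05, one-sample t-test. The noncentral t distribution gives N = 101 for 80% power and N = 135 for 90%, as stated. At N = 102 power is 80.4%, and SE = 1.776/√102 = 0.176.

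**3. How far could the two questions differ?** The documents give neither a stop rate nor a shortfall, so both are assumed. Shift = (net difference in the share of patients stopping early at week 6) × (units by which the stopping score falls below the unseen 3-minute score). With the excess on tiotropium, the contrast is 0.5 − shift:

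| Net share | Shortfall | Contrast | Power, N = 102 |
|---|---|---|---|
| 0 | any | 0.500 | 80.4% |
| 2% | 0.5 | 0.490 | 78.8% |
| 2% | 1 | 0.480 | 77.1% |
| 5% | 0.5 | 0.475 | 76.3% |
| 5% | 1 | 0.450 | 71.7% |
| 10% | 1 | 0.400 | 61.5% |
| 10% | 2 | 0.300 | 39.4% |

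The 2% rows (0.02 × 102 ≈ 2 patients) are taken as the most likely: shifts of 0.01 and 0.02, or 0.01/0.176 = 0.06 and 0.02/0.176 = 0.11 standard errors. Power reaches 75% at a shift of 0.032, which needs a net 3.2% (about 3 patients) at 1 unit or 6.5% (about 7 patients) at 0.5 unit.

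Few stops are expected. Appendix 10.4.2.2 requires a speed the patient has sustained for the full 3 minutes, and Protocol 3.2 has it chosen while long-acting bronchodilators are withheld. The week-6 tests come 2 hours after a dose of active treatment. Stops remain possible, because the highest qualifying speed tried is chosen and then stays fixed.

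**4. The other direction.** With no true effect and the excess of stops on the combination, a shift of 0.01 takes two-sided rejection from 5.0% to 5.04%, 0.02 takes it to 5.15%, and 0.05 to 5.91%. The tail favouring the combination goes from 2.5% to 2.85%, 3.24% and 4.66%.

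**5. What fixed-time comparison is already planned?** The 1, 2 and 2.5-minute endpoints use same-minute baselines and the primary model. Scores observed before a stop are kept, so a stop between 2 and 2.5 minutes leaves the 1 and 2-minute analyses untouched. Only points after the stop are filled by the rule.

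**6. Would an extra analysis at a shared time point be clearly better?** Suppose each patient were scored at the latest minute reached in all of visits 4, 6, 7 and 9. Assume stops fall between 2 and 2.5 minutes and the effect grows in proportion to time. A stop then replaces 0.5 by two thirds of 0.5, so the mean effect is 0.5 × (1 − share/3): 0.497 if 2% of patients have any stop, 0.483 if 10% do. It carries its own dilution, depends on stopping after randomisation, and after a single baseline stop would exchange completed 3-minute week-6 scores for earlier ones.

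**The case for a change.** The strongest case for the concern is that stopping is related to the outcome, so it cannot be presumed harmless. The plan also has little reserve: 102 patients give 80.4% power, with no allowance for dropout. The lower rows of the table show that a large imbalance in stops would matter. A count of early stops by treatment would let a reader see directly that it did not, and an extra analysis fixed before unblinding could not be chosen to suit the result.

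Part of this stands. Equal scores can reflect unequal exercise, the per-protocol repeat is no check on it, and the timed secondary endpoints are only a partial one. A table of stops would be informative. But these points support an optional addition and do not show an error in the plan. The large-shift rows need imbalances that the speed selection makes unlikely. An excess on tiotropium, the likelier direction if the combination works, would understate its benefit. An added descriptive analysis would restore none of the power.

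Nor can the absence be established. Redacted blocks follow the rule in SAP 6.6, an item after SAP 7.4 is not shown, and SAP Table 6.3:1 lists further endpoints whose text is hidden. Some severe stops would also surface in planned reporting: Appendix 10.4.1 provides for withdrawal when a test is stopped for listed symptoms, and Protocol 3.3.4.1 requires withdrawal reasons to be recorded and reported.

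**Conclusion.** The concern does not hold. The SAP rule is the protocol's own endpoint put into practice: the last rating at the end of the test, observed and set in advance. Measured against a hypothetical rating at exactly 3 minutes, the likely difference is 0.01 to 0.02 Borg units, or 0.06 to 0.11 standard errors. Power moves from 80.4% to between 78.8% and 77.1% if stops are commoner on tiotropium. Two-sided rejection under no effect rises to at most 5.15% if they are commoner on the combination. Balanced stops with equal shortfall cancel.

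These sizes rest on an assumed net stop difference of 2%, an assumed shortfall of 0.5 to 1 unit, and the protocol's SD and t-test at 102 patients; the baseline-adjusted model may do somewhat better. The conclusion that the rule is correct does not depend on those assumptions. An extra shared-time analysis or a table of stops is a matter of preference, and following the plan as written would give a sound result.

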#### Rescheduling after randomisation

Subsequent visits should always be planned to take place to assure a minimum 6 week treatment period and a minimum 3 week wash-out period between treatment periods.

If rescheduling of visits after randomisation is necessary, the total daily doses of the Respimat® inhaler need to be obeyed. Reserve medication is dispensed at each treatment period to avoid intermediate visits.

If rescue medication is administered during a visit day within 8 hours prior to administration of trial medication, the visit will be rescheduled once. Further rescheduling should be discussed with the CML.

Refer to sections 4.2.1 and 4.2.2 for details on medications allowed to control acute COPD exacerbations and restrictions for these medications prior to PFTs.

In case a visit needs to be rescheduled outside the allowed time window (e.g. in order to meet PFT wash-out requirements following treatment of an acute exacerbation), the CML should be contacted.

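### Should a Borg score voided by rescue before the exercise test be imputed unfavourably, as SAP 6.6 does after other rescue use?

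*SAP*

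**What the plan says.** SAP 6.6 introduces rescue in this way: "It could happen that a patient needed therapy for COPD symptoms at a clinic visit". It then treats four situations.

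- **Rescue before the exercise test, or at an unknown time.** The trigger is "If rescue medication was used prior to exercise testing or if the time of rescue medication use is unknown". Borg breathing discomfort, blood pressure and IC for that test become missing and stay missing.
- **Rescue during the test.** Borg values after first use are removed and "imputed using the worst non-missing observation during exercise (but not non-missing measurements at rest) for that visit before rescue medication use".
- **Rescue at or before spirometry, or at an unknown time.** Spirometry for the visit is removed, and "In these cases the entire visit will be imputed using the least favourable prior non-missing measurement from previous visits during that period".
- **Discontinuation for worsening.** Completely missing visits due to "worsening of study disease will be imputed with the least favourable prior visit during that period".

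Above these sits a general rule, in Protocol 7.5 and repeated in SAP 6.6: gaps within a visit are filled from that visit's own data, and wholly missing visits go to the statistical model.

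On analysis sets, SAP 6.3 states "Assignment to the FAS will be done after implementation of any data handling rules which set measurements to missing". If the PPS holds fewer than 90% of FAS patients, "the primary analysis for the primary endpoint will also be performed on the PPS as supportive analyses".

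On conduct, Protocol 6.1 states "If rescue medication is administered during a visit day within 8 hours prior to administration of trial medication, the visit will be rescheduled once". Protocol 4.2.1 asks for the exercise test to be rescheduled where possible if rescue is needed on a test day, and Protocol 4.2.2.1 requires an 8-hour washout of short-acting beta-agonists.

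**The concern.** Nearly the same trigger is penalised for spirometry, a secondary endpoint, but not for the Borg score, the primary one. SAP 6.6 reserves the random-missingness assumption for visits that are not missing because of worsening. Rescue taken for COPD symptoms just before a breathlessness test is a plausible non-random cause. If such tests would have scored worse than the model predicts, and fall more often on one treatment, dropping them biases the contrast.

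The unknown-time limb can also discard a valid score, because the rescue may have followed the test. Since the FAS is assigned after values are set to missing, a patient whose only post-baseline Borg score is voided leaves the primary analysis altogether. The PPS analysis changes which patients are included, not how rescue-affected scores are handled, so it would not show any dependence on this rule.

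**Working it through.** **1. The plan's own figure.** Inputs from Protocol 7.7: difference 0.5 Borg units, SD of the within-patient difference 1.776, two-sided alpha 0.05. A one-sample t-test with the noncentral t distribution gives n = 101 for 80% power (0.8001) and n = 135 for 90% (0.9011). Both match the protocol. At the planned 102, power is 80.4%.

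**2. The rules side by side.**

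| Event | Clean exercise data at that visit? | Earlier on-treatment value in the period? | Handling |
|---|---|---|---|
| Rescue during the test | Yes, before rescue | Not needed | Worst pre-rescue exercise score |
| Rescue before the test | No | Uncertain | Left to the model |
| Rescue time unknown | Cannot be identified | Uncertain | Left to the model |
| Rescue at or before spirometry, or time unknown | Not applicable | Yes, by SAP 6.6 (visits 4 to 9) | Least favourable prior value |

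The third column is uncertain for the Borg score because the flow chart marks no shuttle test at visits 5 and 8, while its footnote 14 and Protocol 5.2 describe one. If there is none, the only earlier Borg score in the period is the washed-out pre-dose baseline. Carrying that forward would record no treatment effect for the period.

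The contrast with spirometry is also narrower than it looks. Rescue taken between the 1-hour spirometry and the 2-hour shuttle test leaves spirometry observed.

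**3. Weight of one test.** With 51 patients per sequence, the treatment estimate averages two sequence means of within-patient differences. One test has weight (1/2) × (1/51) = 1/102. Filling a gap with the model's own prediction leaves the estimate unchanged, so filling it d units higher shifts the estimate by d/102. This ignores the small effect of the baseline covariates.

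**4. Size.** Let k be the net number of tests affected on one treatment rather than the other. Both k and d are assumptions.

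- k = 1, d = 1: 1/102 = 0.0098 (2.0% of 0.5)
- k = 2, d = 2: 4/102 = 0.039 (7.8%)
- k = 3, d = 3: 9/102 = 0.088 (18%)
- No imbalance (k = 0): no shift

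**5. What would overturn a result at the planned effect.** SE = 1.776/√102 = 0.1759. The significance limit is t(0.975, 101) × SE = 0.349. Holding the SE fixed, (0.5 − 0.3488) × 102 = 15.4 net test-units, or about 8 net tests at 2 units each, all weighing against the combination.

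**6. Power.** If whole pairs were lost, power would be 79.6% at 100 pairs and 79.2% at 99. These are floors, because the mixed model keeps single-period data.

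**The case for a change.** The best opposing case is that rescheduling does not remove the problem. Protocol 4.2.1 asks for it only where possible. Protocol 6.1 covers rescue in the 8 hours before dosing and reschedules once; it does not reach rescue between dosing and the 2-hour test. The SAP wrote a rule because it expected some cases to remain.

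With larger imbalances the effect is also not trivial. If 15% of tiotropium tests and 5% of combination tests were voided, each 2 units worse than predicted, the shift is 2 × (0.15 − 0.05) = 0.20, or 40% of 0.5. An imbalance of that size on the combination side would exceed the 15.4 test-units above. Nor is the same-visit logic a complete explanation: the discontinuation rule meets the same possible lack of an earlier exercise test, and the flow chart marks no spirometry at visits 5 and 8 either, despite SAP 6.6.

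Part of this stands. The SAP does not state why this case differs, and the PPS analysis does not probe it. Three things limit its force.

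- **The large imbalances are assumed.** Nothing in the documents points to voiding on that scale once tests have been rescheduled.
- **The one indirect clue on direction is reassuring.** Protocol 1.2 reports less daily rescue use on the combination than on its components. If visit-day use followed, more tiotropium tests would be voided and the current rule would understate the combination's benefit. Daily use is not visit-day use, so this is only indicative.
- **Absence cannot be shown.** Text is blacked out inside and around this bullet, and a figure is missing directly after the primary model in SAP 7.4. A further rule or sensitivity analysis may sit there.

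The alternatives are also weak. A fixed penalty has no source in the documents; 2 units would be four times the planned effect. Rescue at an unknown time is no evidence of a worse score at the test.

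**Conclusion.** The rules do differ, but the difference is a fair trade-off. A Borg score taken after rescue is contaminated, so setting it to missing is defensible. With no clean score at that visit and perhaps no earlier on-treatment test, leaving it to the mixed model follows the plan's general rule. Loss from the FAS needs every post-baseline Borg score of a patient to be voided, and a patient with one period adds little to a within-patient contrast. A missing period baseline at visit 4 or 7 is already imputed from the other period, so the issue is confined to visits 6 and 9.

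For a net imbalance of up to 3 tests and an excess of 1 to 3 units, the shift is 0 to 0.088 Borg units; about 15.4 net test-units are needed to bring an observed 0.5 to the limit. This rests on affected tests being few, which the rescheduling provisions make likely but the documents do not quantify. The direction cannot be settled from the documents.

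A count by treatment of voided visit 6 and 9 tests would be a natural addition to the summary of pulmonary medication use planned in SAP 7.2. That is a reporting choice; the primary conclusion does not depend on changing the plan.
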